Demographics	X				
Brief physical examination	X				
Pregnancy test for females*	X				
Laboratory tests: Serum creatinine and AST and ALT laboratory *	X				
Neuropsychiatric Inventory	X		X	X	X
TBI-QOL Anger	X		X	X	X
SASNOS	X		X	X	X
AIIM	X				X
PHQ-9	X		X	X	X
GAD-7	X		X	X	X
PCL-C	X				
GOS-E	X				
Clinical Global Impressions	X		X	X	X
Global Impression of Change			X	X	X
Working Alliance Inventory-Short Revised (WAI-SR)					X
Summary Questionnaire (Subject)					X
Summary Questionnaire (Observer)					X
Record concomitant meds	X	X	X	X	X
Study Completion Form*****		X			
Assign study number**	X				
Randomization**	X				
Review proper medication use**	X	X	X	X	X
Dose adjustment**		X	X	X	X
Dispense drug**	X		X	X	X
Pill count**			X	X	X
Record adverse events**		X	X	X	X

* These steps only performed if meets all eligibility criteria up to that point

** These steps only performed if meets all eligibility criteria

*** Calls weekly

**** Complete after telephone call 131

***** Optional

Drug Accountability: Compliance is enhanced through pill organizers, medication diaries, and frequent contacts (weekly contact). In the event that study personnel learn that a subject has not complied with the dosing schedule, the RA will try to resolve any concerns and encourage continuation in the study taking all doses as prescribed. The lack of compliance will be recorded on the relevant drug accountability case report form (CRF) for that subject.

Compliance: Pill counts will be performed at each visit. Compliance will be considered at least 75% medication consumption. If study medication compliance is at least 75% and not more than 125% over the course of the entire study, this will be considered compliant and would not represent a protocol deviation.

6.1/2 REPORTING OF ADVERSE EVENTS OR UNANTICIPATED PROBLEMS INVOLVING RISK TO PARTICIPANTS OR OTHERS

Side Effects and Adverse Events: All AEs encountered during the study will be recorded beginning at the time the informed consent form is signed. Participants will be encouraged to report each AE, and will be queried about AEs with each contact. All clinically significant changes in health status will be recorded and followed, including the date and time of onset, severity, relationship to study medication, the date of resolution (or the fact that the event is still continuing), the action taken, and the outcome. The PI will categorize each AE according to its severity (mild, moderate, severe) and suspected relationship to the study treatment. AEs not resolved at the completion of a protocol are followed until resolution or for duration as deemed appropriate by the Data Safety Monitoring Board (DSMB). Serious adverse events (SAEs) will be reported to the local IRB within 24 hours of the project staff becoming aware of the event. A study pager and call schedule will be maintained to assure timely communication.

Clinical and Safety Monitoring: The PI, Project Manager, Clinical Monitor, and DSMB, all with the training and experience to oversee the study conduct, will monitor the study in accordance with Good Clinical Practices. A Clinical Monitor from the Indiana CTSI will review record accuracy and completeness, check source documents, and evaluate study data (drug accountability, communication, and written records). The DSMB will monitor the study for purposes of safety and integrity, which will include review of AEs, SAEs, protocol deviations and violations, and data quality reports. A Manual of Procedure will be developed that specifies our procedures that guide dose adjustment and management of AEs, SAEs, and suicidal ideation.

7.1/2 STUDY WITHDRAWAL/DISCONTINUATION

Subject Withdrawal: Subjects may discontinue or withdraw from the study for any of the following reasons: (1) subject's request, (2) adverse event requiring treatment discontinuation, (3) investigator deems necessary. If a subject withdraws or is discontinued for any reason, they will be asked if they will return to the site as soon as possible where all Final Visit assessments will be conducted as is necessary for an intent-to-treat analysis.

Termination of the Study: If the PI or DSMB discovers conditions arising during the course of the study which indicate that the clinical investigation should be halted, the study may be terminated after appropriate consultation and discussion. Conditions that may warrant study termination include, but are not limited to, the discovery of a significant, unexpected and unacceptable risk to the subjects, failure to enroll subjects at an acceptable rate, insufficient adherence to the protocol requirements, or completion of study objectives.

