2.0 PROJECT RATIONALE AND SPECIFIC AIM

For the present project we have chosen to study a treatment for irritability and aggression (*buspirone*) and refine measurement of the *impact* of irritability and aggression (a separate study protocol). There are many other medications that may reduce irritability and aggression, and thus, this effort is only part of an ongoing, systematic approach to build an evidence-base to guide informed decision making. The investigators are committed to studying the effect of additional medications in the future, as well as continuing comprehensive, systematic study of post-TBI irritability and aggression. The current work fits additional pieces into a complex puzzle to address the treatment of these problematic behaviors. This body of work supports the priorities of the NIDRR Long-Range Plan ⁷⁰ through the production of new scientific knowledge through research into pharmacologic interventions that can be used to improve options for achieving independence, social involvement, and function.

Specific Aim: Decrease irritability and aggression expressed by persons with TBI through the assessment of buspirone effectiveness for post-traumatic irritability and aggression and development of an irritability/aggression impact measure.

Target population: Persons with irritability and aggression following TBI and their families.

TREATMENT AND PLACEBO ARM:

“BUSPIRONE FOR THE TREATMENT OF CHRONIC POST-TBI IRRITABILITY & AGGRESSION: A 91-DAY SINGLE-SITE, FLEXIBLE-DOSE, PARALLEL GROUP, RANDOMIZED, DOUBLE-BLIND, PLACEBO-CONTROLLED TRIAL”

BuSpar® (buspirone) was introduced in the United States by Bristol-Myers Squibb in 1986 as a novel anxiolytic, receiving FDA approval for the treatment of Generalized Anxiety Disorder (GAD). Since the patent expired in 2001, BuSpar has been available in generic form. BUSP is an anxiolytic psychoactive drug of the azapirone chemical class that is unrelated pharmacologically to benzodiazepines, barbiturates, or other sedative and anxiolytic agents. Numerous studies in non-TBI populations have shown equivalent efficacy of BUSP and the benzodiazepines in treating GAD, and confirmed the preferential side effect profile of BUSP.

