- **St Andrew's-Swansea Neurobehavioural Outcome Scale (SASNOS):**¹¹⁵ SASNOS is a newly developed informant-rated measure designed specifically to assess neurobehavioral dysfunction in acquired brain injury as rated by an observer. SASNOS has a 5-factor conceptual framework based on the World Health Organization International Classification of Function (WHO ICF) that allows the measurement of a diverse range of NBD signs and symptoms in the following domains: interpersonal relationships, cognition, aggression, inhibition and communication. Initial validation suggests that the 49-item SASNOS is reliable and valid. The proposed study will utilize the aggression subscale, which includes 15 items and three subfactors: overt aggression (3 items), irritability (6 items), and provocative behavior (6 items). The aggression subscale demonstrates excellent test-retest reliability (ICC=.92) and internal consistency (alpha=.92), good inter-rater reliability (ICC=.80), and a strong statistical relationship with known measures, supporting its content, convergent, and divergent validity.

- **Global Impression of Change (GIC):** A Likert Scale rating impression of change (much improved, slightly improved, no change, slightly worse, or much worse) will be used for both participants and observers to rate their impression of change in the person with TBI.

- **Clinical Global Impressions (CGI):** The clinician's impression of change will be determined using the CGI. The CGI¹⁵⁸ is a highly sensitive,¹⁵⁹ standardized assessment tool used widely to assess psychopharmacology treatment response. The CGI is comprised of 3 subscales: Severity of Illness (SI), Global Improvement (GI), and Efficacy Index (EI). SI and GI are both rated on 7-point scales. The EI is rated on a 4-point scale that takes into account both beneficial effects and side effects. The CGI is rated by a clinician/investigator. The SI subscale is administered at initial assessment and then all three subscales are administered at follow-up assessments. To be considered effective, a treatment should lower the overall score in subsequent testing by at least 50%.¹⁶⁰ The CGI takes approximately 2 minutes for the clinician to score.

Experimental Measure (this measure to be developed after study completion, and thus, will be delayed in time from final analysis)

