- **Aggression and Irritability Impact Measure (AIIM):** The AIIM is an experimental measure that will be developed and evaluated through the companion measurement study. It will consist of items assessing the degree to which irritability or aggression interferes with community participation activities. Specific community participation activities will be represented by items of the Participation Assessment with Recombined Tools-Objective (PART-O).¹⁶¹ Additional items may be added after focus group review and cognitive interviewing that will take place prior to launching the study. The AIIM will be designed to assess specifically the degree to which irritability and aggression interfere with participation in contrast to the PART-O which assesses the extent of community participation in general. The beta version of the AIIM will be included in this Buspirone treatment study. It will be administered at the Baseline and Final visits as it is thought that the longer period is needed to allow time for changed impact. After refining it through psychometric studies, the final version of the AIIM will be extracted from the Beta version and analyzed as a dependent measure in the treatment arm to assess its responsiveness to the hypothesized treatment effect. The AIIM is included in the treatment arm only to assess its responsivity and not as an endpoint.

- **Working Alliance Inventory-Short Revised (WAI-SR):** The WAI-SR is a 12 item questionnaire with forms for completion by the person receiving treatment as well as by the provider. This measure of working or therapeutic alliance has been shown to predict the outcome of psychotherapeutic as well as rehabilitation interventions.²¹⁹ The WAI-SR is based on a factor analysis of the full WAI and has demonstrated reliability and validity.²²⁰ The WAI-SR will be completed during the post-treatment assessment session at the end of the buspirone trial by the participant and by the research assistant who worked with the participant in the trial. Each of these individuals will complete the inventory independently without knowledge of each other's responses. Data obtained from the WAI-SR will be evaluated as a covariate in analyses of outcome variables to assess for effects of buspirone relative to placebo.

Stratification Measure

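### The trial's only stated test of AIIM responsiveness is the buspirone effect, so a null or small drug effect would leave that question unanswerable as planned

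*Combined protocol and SAP*

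**What the plan says.** Section 5.1 of the combined protocol and SAP, under the AIIM entry, limits the instrument's role: "The AIIM is included in the treatment arm only to assess its responsivity and not as an endpoint". The final version, extracted from the beta version after psychometric refinement, is to be "analyzed as a dependent measure in the treatment arm to assess its responsiveness to the hypothesized treatment effect". On timing: "It will be administered at the Baseline and Final visits". The heading above the entry says that the measure will be developed after the study is complete, so its analysis comes later than the final analysis.

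Development is placed elsewhere. The same entry calls the AIIM an "experimental measure that will be developed and evaluated through the companion measurement study", and Section 2.0 says that the impact-measurement work has its own protocol. The Specific Aim in Section 2.0 names "development of an irritability/aggression impact measure" and does not mention responsiveness. The Primary and Secondary Aims in Section 2.1 do not mention the AIIM.

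Section 8.1 has no AIIM analysis: no reference measure of change, no criterion for calling the AIIM responsive, and no fallback if buspirone does not work. It has only a general allowance for further exploratory analyses.

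Possible reference measures are already collected. The visit lists and the Schedule of Events put the NPI and the AIIM at Visits 1 and 4. The Global Impression of Change (GIC), which "will be used for both participants and observers to rate their impression of change in the person with TBI", is collected at Visits 2 to 4.

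**The concern.** A responsive measure moves when the patient's condition moves. The plan ties that judgement to an effect that the trial exists to test, and Section 2.0 says that no rigorous study of buspirone for post-TBI irritability or aggression has been published. A null or small effect is therefore a real possibility. A flat AIIM comparison would then have two explanations that the planned analysis cannot separate.

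The phrase 'treatment arm' adds to the problem. Section 1.0 speaks of two study arms, and Section 2.0 uses the word for the drug trial as opposed to the measurement study, so the phrase may mean the whole randomised trial. It may also mean the buspirone group alone. In that case change in AIIM is mixed with placebo response and natural course, and the bias runs the other way.

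At stake is the AIIM's one stated purpose in this trial. Because the analysis follows the final efficacy analysis, a criterion left open could also be chosen with the efficacy result in hand.

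**Working it through.** **Inputs from Section 8.1.** 33 per group analysed (66 in total) and 37 per group enrolled; 40% versus 80% responders with 90% power; P(Y>X) = 0.70 with 80% power for the secondary Wilcoxon tests; alpha 0.05, taken as two-sided because the plan does not say. The plan gives no figure for the AIIM.

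**The plan's own figures.** Noether's formula: N = (1.96 + 0.84)² / [12 × 0.25 × (0.70 − 0.50)²] = 65.4, or 32.7 per group, so 33. For 40% versus 80% at 90% power, the two-proportion formula gives 30 per group without continuity correction and 35 with it; 33 lies between, with power about 93% (uncorrected). 33/0.9 = 36.7, so 37. The stated sample size reproduces.

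**Step 1: chance that a sound AIIM shows a significant buspirone-placebo difference.** For a Wilcoxon test with 66 analysed, z = √(12 × 0.25 × 66) × (P − 0.5) = 14.07 × (P − 0.5), and power = Φ(z − 1.96) + Φ(−z − 1.96).

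| True P(Y>X) on AIIM | Chance of significance |
|---|---|
| 0.50 (no drug effect) | 5% |
| 0.55 | 11% |
| 0.60 | 29% |
| 0.65 | 56% |
| 0.70 | 80% |

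**Step 2: the buspirone-only reading.** If 40% is the rate without a drug effect (an inference, since Section 8.1 does not name the group), then 0.40 × 33 = 13.2, so about 13 of 33 buspirone participants would still drop 3 or more NPI points with an inert drug. The AIIM could show change in that group with no drug effect.

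**Step 3: between-group test against a pooled responder comparison.** Let g be the difference in mean AIIM change, in within-group SDs, between NPI responders and non-responders. The documents give no value for g, so it is varied. Assume that the drug acts on the AIIM only through responder status.

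- Between groups at 40% versus 80%: the difference is 0.4g and power = Φ(0.4g × √(33/2) − 1.96).
- Pooled: responders are 13.2 + 26.4 = 39.6, about 40, against about 26 non-responders. Power = Φ(g × √(40 × 26/66) − 1.96) = Φ(3.97g − 1.96).

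| g (assumed) | Between-group | Pooled responder |
|---|---|---|
| 0.3 SD | Φ(0.49 − 1.96) = 7% | Φ(1.19 − 1.96) = 22% |
| 0.5 SD | Φ(0.81 − 1.96) = 13% | Φ(1.98 − 1.96) = 51% |
| 0.8 SD | Φ(1.30 − 1.96) = 25% | Φ(3.18 − 1.96) = 89% |
| 1.0 SD | Φ(1.62 − 1.96) = 37% | Φ(3.97 − 1.96) = 98% |

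Allowing for the extra variance from mixing responders and non-responders within a group lowers 25% to about 23%.

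With 40% responding in both groups there are about 26 responders and 40 non-responders. The product 26 × 40 is unchanged, so the pooled column stays the same while the between-group test falls to 5%.

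**Step 4: a second anchor.** Correlating AIIM change with NPI change in all 66 (Fisher z, Φ(atanh(r) × √63 − 1.96)) has power 36%, 69%, 92% and 99% at assumed true correlations of 0.2, 0.3, 0.4 and 0.5. This needs no drug effect either.

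**The case against.** The strongest reply is that the plan claims something narrower. It proposes to examine response to this treatment, a property that a randomised trial can address, and it uses the idea consistently: Section 1.0 credits the NPI domains with responding to the interventions studied, and the NPI entry in Section 5.1 cites their separation of drug from placebo in the amantadine trial. On this view an anchor-based definition is partly a reviewer's preference. That usage does help if buspirone works. It gives no answer if buspirone does not, and the plan has no fallback.

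The companion protocol is not among the documents and may contain its own responsiveness plan. The Section 5.1 summary table lists the AIIM, the observer NPI, SASNOS and TBI-QOL Anger for that study too. This stands as a limit: the point concerns what this document specifies.

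The power contrast depends on its model. Part of the between-group disadvantage comes from assuming that the drug reaches the AIIM only through a dichotomised NPI response; under the plan's own P(Y>X) = 0.70 the between-group test has about 80% power. The pooled test is also weak if the gap is small. Both points stand, and the figures are given only as a range.

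Finally, the data are collected anyway and Section 8.1 allows exploratory analyses, so nothing is lost for good. That is true, but an analysis chosen after the efficacy result is known does not replace a criterion fixed beforehand.

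**Conclusion.** The point holds for the responsiveness question in this trial. The one stated criterion depends on the drug's efficacy. With no drug effect a sound AIIM would show a significant between-group difference about 5% of the time, and with a small effect (P(Y>X) of 0.55 to 0.60) 11% to 29%. A negative result could not separate a poor measure from an ineffective drug; under the buspirone-only reading, a positive result could not separate drug effect from placebo-type improvement.

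Four stronger readings are tempting and are not supported:

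- That part of the Specific Aim would go unanswered. The aim names development of the measure, and the documents assign that to the companion study.
- That a null result would be recorded as an unresponsive AIIM. Section 5.1 states no pass/fail rule.
- That 25% versus 89% describes this plan. It follows from an assumed 0.8 SD gap and one model of how the drug acts.
- That the plan states 40% as the placebo rate. Section 8.1 says only that one group has it.

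The AIIM is not an endpoint, so efficacy and safety conclusions are unaffected. The change is worth making and is not critical to the trial.

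**What to change.** In the AIIM entry of Section 5.1, with a cross-reference in Section 8.1:

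1. State that 'treatment arm' means the whole randomised trial.
2. Prespecify responsiveness in both groups pooled: compare AIIM change from baseline to Day 91 between participants who do and do not reach the 3-point observer NPI Irritability decrease, and across observer and participant GIC categories. Report the correlation of AIIM change with NPI change.
3. Report the buspirone-placebo AIIM difference separately as exploratory, and not as the test of the measure.
4. Report observer and participant AIIM versions separately, because an anchor that shares a rater with the AIIM may inflate agreement.

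The cost is wording and a little more analysis. No new data are needed: AIIM and NPI are collected at Visits 1 and 4, and GIC at Visit 4. If the companion protocol already contains such a plan, a reference to it would serve, provided it was fixed before the efficacy result is known.

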Stratification: Randomization will be stratified on the presence of major or minor depression (defined by PHQ-9 total score ≥ 5) to ensure equal distribution of depression in the BUSP and placebo groups. This is important since depression is common after TBI, irritability is a primary symptom of depression, and BUSP has potential effect on depression. The study is not designed or powered to examine the effect of BUSP on depression. Participants will

have a 1:1 chance of receiving placebo or active treatment regardless of depression status. Our statistician will create a guide that assists the study pharmacist in the process of carrying out the stratified randomization.

Randomization: After successful screening, enrollment, and stratification, each participant will be assigned a study identification number that determines the double-blind treatment group according to the chronological order of entry into the study. Random assignment to either BUSP or placebo will be based on a computer-generated, block, randomization schedule produced by the statistician and maintained by the study pharmacist. Randomization will be blocked to force balance between the 2 groups (important if the study were stopped). The investigators and study staff will be blinded to the size of the blocks. Upon meeting all eligibility criteria, the RA will fax a completed randomization sheet to the study pharmacist that indicates the information needed for dispensing and stratification (study number, and total PHQ-9 score). The study pharmacist then looks at the randomization schedule and prepares the study medication to be dispensed. The study pharmacist will record the group assignment in the dispensing log.

Compensation: To help offset time and travel costs, participants and their observer will both receive \$50 for the initial formal screening and \$50 for the subsequent visits. Compensation will be provided in the form of check or gas gift card.

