NPI Irritability domain rated by observer. NOTE: The primary analysis looks at the proportion that decrease ≥ 3 points to assess clinical significance in addition to statistical significance. This cut point of clinically meaningful change is based on clinical experience and

consumer input, and was utilized in our previous studies. A secondary analysis compares changes in NPI-Irritability using an ordinal scale.
Secondary Efficacy Measures
NPI- Irritability domain rated by observer and participant
NPI-Distress Irritability domain rated by observer and participant
NPI & NPI-Distress Agitation/Aggression Domain rated by observer and participant
TBI-QOL Anger item bank rated by participant
SASNOS rated by observer
Global Impression of Change rated by observer and participant
Clinical Global Impressions rated by clinician
Working Alliance Inventory – Short Revised rated by participant and Co-Investigator.

Demographic and Pre-treatment Characteristics: Age, gender, marital status, ethnicity, educational level, time since injury, history of psychiatric disorder, previous TBI, cause of injury, CT scan findings, initial Glasgow Coma Scale score in ED, duration of post-traumatic amnesia (PTA), duration of loss of consciousness, socioeconomic status, employment status, substance use during the month prior to enrollment, relationship of observer to subject, medical history, overall function, severity of irritability, and presence of depression, anxiety or post-traumatic stress disorder (PTSD).

Efficacy Measures:

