8.1 STATISTICAL CONSIDERATIONS

General Considerations: Statistical analyses for this study will be the responsibility of the study statistician working through the Department of Biostatistics. Safety and efficacy analyses will be conducted on all evaluable patients. Parameter estimates and relevant summary statistics will be reported where appropriate. For continuous variables, summary statistics will include number of patients, mean, median, standard deviation, minimum and maximum. Categorical variables will be summarized using number of patients, frequency, and percentages. Additional exploratory analyses of the data will be conducted as deemed appropriate. Changes from this analysis plan will not require an amendment to the protocol unless it changes a significant feature in the protocol. The statistical analysis methods are detailed below. Standard statistical methods will be employed. Descriptive statistics, including means and standard deviations, or counts and percentages will be calculated. As a majority of the outcome variables are measured on the ordinal (Likert) scale, nonparametric statistical tests will be employed. The SAS® software, version 9.3,¹⁶⁶ will be used. A p-value of less than 0.05 will be considered statistically significant unless otherwise noted. Analysis plans specific to each hypothesis are further discussed below.

Analysis Sets: The definitions of the study populations are listed below:

Population	Definition
Intention-to-Treat	All patients who meet the eligibility criteria and are registered for the study irrespective of their compliance to the planned course of treatment.
Per Protocol Set	All patients who complied with the protocol sufficiently to ensure that these data would be likely to exhibit the effects of treatment, according to the underlying scientific model. Compliance covers such considerations as exposure to treatment, availability of measurements and absence of major protocol violations.

Population	Definition
Safety	All patients receiving at least one dose of study drug are included in the analysis of safety, unless otherwise noted.

Participant Characteristics: Participant demographics and baseline characteristics will be listed and summarized for the Intent-to-Treat population, including age, gender, ethnicity, height, weight and medical history.

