Hypothesis 1b: Among individuals with TBI of >6 months duration, BUSP will result in statistically significant improvement in scores of one or more of the following measures compared to placebo: a) observer and participant ratings of NPI and NPI-Distress Irritability domain scores, b) observer and participant ratings of NPI and NPI-Distress Aggression domain scores, c) participant ratings of TBI-QOL Anger bank, d) observer ratings of SASNOS, e) observer and participant ratings of Global Impression of Change, f) physician ratings of Clinical Global Impressions.

The primary analysis will be intention-to-treat. For Hypothesis 1a, the primary outcome, the percent of participants who are considered to have meaningful reduction in irritability (decrease of at least 3 points in the NPI Irritability Domain Score) from baseline to 91 days, will be compared between the two groups (those receiving active drug and

placebo) using a chi-square test. A logistic regression model will be used to adjust for depression and possible demographic and baseline differences between the two groups and a post-hoc secondary analysis will examine the factors (including depression and anxiety) influencing the effect of BUSP on the primary outcome by including group interaction in the logistic model. For Hypothesis 1b, the change in the observer-rated NPI Irritability Domain Score from baseline to 91 days will be compared between the two groups using a Wilcoxon rank sum (Mann-Whitney) test for ordered categories. The secondary outcomes will also be compared between the two groups using Wilcoxon rank sum tests. For the secondary outcomes, Hochberg's step-up Bonferroni method will be used to control for multiple testing. Secondary analyses will include repeating the analyses above using the PPS population. Wilcoxon rank sum tests will also be performed for separate subgroups such as females, males, participants with injury caused by motor vehicle crashes or falls to test whether BUSP can be efficacious for these separate subgroups. In addition, if a substantial number of participants have depression, a preliminary analysis of the effect of BUSP on PHQ-9 may be performed. The effect of BUSP on GAD-7 will also be performed.

Safety Analysis: Hypothesis 2: BUSP will be tolerated as measured by number and types of the adverse events in the treatment group compared to the placebo group.

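### The Working Alliance Inventory is scored only at the Day 91 visit, yet the protocol plans to use it as a covariate when estimating buspirone versus placebo

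*Combined protocol and SAP*

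**What the plan says.** The WAI-SR entry in section 5.1 (Study Procedures) fixes the timing: "The WAI-SR will be completed during the post-treatment assessment session at the end of the buspirone trial by the participant" and, independently, by the research assistant. The Study Sequence and the Schedule of Events agree, showing it at Visit 4 and at no other visit. The same entry gives its use: "Data obtained from the WAI-SR will be evaluated as a covariate in analyses of outcome variables to assess for effects of buspirone" relative to placebo. It names no model, no outcome and no choice between the two raters' scores, and it says that alliance has been found to predict outcome in other interventions.

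Section 8.1 does not mention the WAI-SR. The primary test is an unadjusted chi-square, followed by this: "A logistic regression model will be used to adjust for depression and possible demographic and baseline differences between the two groups". For the rest, "The secondary outcomes will also be compared between the two groups using Wilcoxon rank sum tests", and Hochberg's "step-up Bonferroni method will be used to control for multiple testing". A general clause adds: "Additional exploratory analyses of the data will be conducted as deemed appropriate".

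The outcome list in section 5.1 places the WAI-SR among the secondary efficacy measures, "rated by participant and Co-Investigator". Hypothesis 1b (sections 2.1 and 8.1) lists its measures a) to f) without it. The second rater is the Co-Investigator in the outcome list, but the research assistant in the WAI-SR entry and in the Summary of Measures table.

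**The concern.** Randomisation makes the arms comparable on what precedes it. A score taken after 91 days of drug or placebo, alongside the outcome, has no such protection. If improvement raises the rating, adjusting for the rating removes part of the effect being estimated. If the drug moves the rating by another route, such as side effects, and the rating is related to outcome, adjustment can create an effect where none exists, in either direction.

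The sentence could mean no more than checking whether alliance is associated with outcome, but it ties the covariate to assessing buspirone against placebo. The general clause on exploratory analyses does not label this one exploratory. An adjusted result could therefore be reported beside the primary result, with the protocol's authority, and disagree with it.

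A second, smaller matter is that the same score is listed as an efficacy outcome and planned as an adjustment variable, so its membership of the Hochberg family is undefined.

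**Working it through.** **Inputs from the documents.** Section 8.1, Sample Size: 40% versus 80% responders, 33 per group, 90% power, alpha 0.05 (taken as two-sided), 10% loss, 37 per arm. No WAI-SR correlation or arm shift is given, so these are assumed and varied.

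**The plan's own figure.** With mean proportion 0.6, n per group = [1.960 × √(2 × 0.6 × 0.4) + 1.282 × √(0.4 × 0.6 + 0.8 × 0.2)]² / 0.4² = (1.358 + 0.810)² / 0.16 = 29.4, so 30, or 35 with continuity correction. The stated 33 lies between them; uncorrected power at 33 is 93.1%. Noether: (1.960 + 0.842)² / (12 × 0.25 × 0.2²) = 65.4 in total, so 33 per group. Then 33 / 0.9 = 36.7, so 37. The figures hang together, and 33 per arm is used below.

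**Model.** Latent improvement L = μ(arm) + e, with e standard normal; a responder has L > 0. For 40% and 80%, μ = −0.253 and 0.842, so d = 1.095. WAI-SR = ρL + √(1 − ρ²)u + δ × arm. On the latent scale the arm effect adjusted for WAI-SR is

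d − ρ(ρd + δ) = d(1 − ρ²) − ρδ.

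The first term shrinks a real effect and the second can create a false one. For responders, a logistic model with arm and WAI-SR was simulated: 40,000 trials of 33 per arm per case, two-sided Wald test at 0.05, and the standardised risk difference from a fit to 2,000,000 simulated participants.

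**Case 1: true effect, rating reflects improvement (δ = 0).** Without WAI-SR the difference is 0.40 and rejection is 93.0–93.4%.

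| ρ | d(1 − ρ²) | Adjusted risk difference | Rejection | Arm comparison of WAI-SR detects its shift |
|---|---|---|---|---|
| 0.1 | 1.084 | 0.396 | 92.3% | 7.2% |
| 0.2 | 1.051 | 0.385 | 91.3% | 14.0% |
| 0.3 | 0.996 | 0.367 | 88.4% | 25.7% |
| 0.5 | 0.821 | 0.301 | 77.0% | 58.8% |
| 0.7 | 0.558 | 0.202 | 52.0% | 86.4% |

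**Case 2: no true effect, δ = 0.** The formula gives 0. Simulated differences are within 0.001 of 0, and rejection is 5.0%, 5.1% and 4.8% at ρ = 0.3, 0.5 and 0.7.

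**Case 3: no true effect, rating 0.3 SD lower on buspirone (δ = −0.3).** The formula gives 0.09, 0.15 and 0.21 at ρ = 0.3, 0.5 and 0.7. The false difference is 3.5, 5.7 and 8.0 points; rejection is 6.0%, 7.8% and 11.4%. An arm comparison finds the shift in about 22–23% of trials. A shift of +0.3 reverses the sign.

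**Case 4: rating not moved by treatment or by the gain it produces.** The difference stays at 0.40.

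**Second check with different scaling.** WAI-SR = b × L plus noise of SD 1, with b = 0.3, 0.5 and 1.0, which is correlation b/√(1 + b²) = 0.29, 0.45 and 0.71. Adjusted differences are 0.37, 0.32 and 0.20. Power falls from about 94% to 90%, 82% and 54%. The two runs agree.

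**Hochberg family.** Hypothesis 1b: NPI and NPI-Distress irritability by two raters, 4; the same for aggression, 4; TBI-QOL 1; SASNOS 1; Global Impression of Change 2; CGI 1 as one score or 3 as subscales. The total is 13 or 15. Two WAI-SR raters make it 15 or 17. The strictest step moves from 0.05/13 = 0.0038 to 0.05/15 = 0.0033, or from 0.0033 to 0.05/17 = 0.0029.

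**The case against.** No analysis specified in section 8.1 is affected. The chi-square and Wilcoxon tests take no covariates, and a Day 91 score is not a baseline difference, so it cannot enter the stated logistic model. That stands, and it limits the weight of the point. It does not withdraw the analysis announced in section 5.1.

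The WAI-SR entry follows a heading for an experimental measure. That heading is singular and its note describes the irritability impact measure (AIIM), so it is weak evidence that the WAI-SR analysis is exploratory.

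Blinding (section 5.1) should stop knowledge of assignment from moving either rater, and the side-effect differences in section 2.0 are modest (nausea 8% versus 1%, dizziness 3% versus under 1%). This makes case 3 less likely; nothing in the documents supports a 0.3 SD shift. Blinding does not stop improvement from moving the rating, so case 1 remains.

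The observer rates the primary outcome, while the participant and a staff member rate the WAI-SR, so low correlations deserve weight. At 0.1 to 0.2 the bias in case 1 is negligible, and in case 3 it is about 1.1 to 2.5 points with rejection still about 5%. If the rating were a stable trait that treatment does not move, adjustment would even raise power, from about 94% to 94%, 97% and 98% at 0.3, 0.5 and 0.7. All of this is fair, but the trial cannot establish which case it is in. Because "Random assignment to either BUSP or placebo will be based on a computer-generated, block, randomization schedule", comparing the WAI-SR by arm is a valid check on whether treatment moves it, but at 33 per arm that check often lacks power. Without a baseline score, a stable trait cannot be fully separated from a consequence of improvement.

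The multiplicity effect is small, and the count could be 12 if observer-rated NPI irritability is held apart from the other secondary outcomes.

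**Conclusion.** The concern holds. As written, section 5.1 adjusts a treatment comparison for a score collected after randomisation, at the same visit as the outcome. Whether this biases the result, and by how much, depends on quantities the documents do not give. Over assumed correlations of 0.1 to 0.7, with a rating that reflects improvement, a true 40-point difference is estimated as about 40 down to 20 points; 0.7 is a high case given the different raters. With no true effect, a rating that follows improvement alone produces no false positives; an assumed direct 0.3 SD shift produces rejection of about 6% to 11% at correlations of 0.3 to 0.7.

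The primary conclusion is not at risk. What needs correcting is a stated rule that could yield a conflicting adjusted estimate not labelled exploratory. It should be fixed before analysis. The WAI-SR's status as a secondary outcome is a labelling conflict of minor consequence, and the second-rater mismatch is editorial.

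**What to change.** Replace the covariate sentence in the WAI-SR entry of section 5.1 with: *Because the WAI-SR is collected after randomisation, it will not be used as a covariate in the analyses that estimate the effect of buspirone versus placebo. Its association with Day 91 outcomes, and any mediation analysis with its assumptions stated, will be reported by rater and labelled exploratory.*

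In section 8.1, state that models estimating the treatment effect adjust only for pre-randomisation variables: the depression stratum, the baseline score, and the demographic and baseline variables already allowed there.

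Remove the WAI-SR from the secondary efficacy list in section 5.1 so that the list matches Hypothesis 1b and the Hochberg family is clear. Keeping it as an outcome expressly outside that family would also reconcile the text. Make the second rater the same throughout.

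The cost is protocol and SAP wording. No data, visits or sample size change, and the question about alliance can still be studied.
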